1.3 Study design and settings

This study will be a site-based retrospective non-interventional medical chart review of pediatric and adult male and female patients with PROS.

Patients with PROS who have received at least one dose of alpelisib initiated at least 24 weeks before the cutoff date (09-Mar-2020) through a Novartis Managed access program (MAP) and satisfy the study inclusion criteria will be included in the study.

Patient-level data will be abstracted from medical charts of all eligible patients at all participating sites and will be pooled and assessed. Trained personnel at each site will abstract medical chart data. Informed consent will be obtained prior to data abstraction, as appropriate, for eligible patients interested in participating in the study where required.

[figure not shown]
The cut-off date of 09-Mar-2020 is selected to minimize the impact of the COVID-19 pandemic on the data integrity. Eligible patients who were initiated alpelisib on or before 23-Sep-2019 are expected to have 24 weeks of relevant assessments on or before 09-Mar-2020. At that time of the cut-off, COVID-19 pandemic did not have major consequences on the regular management of the patients in the countries participating in the MAP.

The **study period** will be defined as the period from the index date up to the cut-off date (09-Mar-2020) (Figure 1-1). During the study period all available data will be collected, if a patient has discontinued treatment prior to the cut-off date only data reported up to 30 days after the last date of study treatment will be abstracted and entered into the database.

The **index date (baseline)** will be defined as the date of alpelisib initiation. This date will be used as reference date for all assessments (safety and efficacy).

The **pre-index date** period will be defined as the period from up to 24 weeks prior to the index date (baseline) through to the day prior to the index date. (Figure 1-1).

Figure 1-1 Study design

Lesion assessments and definition

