3.2 Analysis population(s)

The **full study population** will include all patients that satisfy the study inclusion criteria. This population set will be used for all secondary [REDACTED] efficacy analyses and for safety analyses.

The **efficacy population** is a subset of the full study population, which will be used for the analysis of the primary endpoint and includes patients who meet the following criteria:

- Patient had at least one target lesion
- Patient had an imaging scan performed on the index date (or up to 24 weeks prior to the index date) for at least one target lesion

3.3 Key post index date time points for reporting endpoint over time.

Considering the retrospective nature of the study, patients might have data available at different time-points. In order to maximize the use of data abstracted, key time points and associated time windows are identified for reporting purpose. For each of these time-points or intervals all patients with data available will be used. The total number of patients in a time interval will be equal to the number of patients with at least one valid assessment in that specific time window. The number of patients (N) in each interval will be summarized in the disposition table and used throughout the report. Only the time points with data available for at least 10% of the patients will be displayed in the corresponding output.

Key study time points are summarized in [Table 3-1](#).

Table 3-1 Time windows for post-index date key-time point

Key time-points	Allowed windows
4 weeks	Up to 10 weeks
12 weeks	[10 to 20 weeks[
24 weeks*	[20 to 32 weeks[
36 weeks	[32 to 40 weeks[
52 weeks	[40 to 58 weeks[
End of study	4 weeks prior to and up to min(study treatment discontinuation + 30 days, cut-off date)

* 24 weeks or 6 months (+/- 4 weeks).

After week 52 intervals of approximately 11 weeks (e.g. 63 weeks, 74 weeks, etc.) with a time window of +/- 5 weeks will be used until the "end of study".

Week 24 windows (+/- 4 weeks) is intended to include assessments performed 24 weeks or 6 months after index date, where 6 months is approximated to week 27.

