3.6 Secondary endpoints

Secondary endpoints will be used to support the efficacy of alpelisib, to provide a more complete description of the impact of alpelisib on the heterogeneous manifestations of PROS and to evaluate the safety and tolerability of alpelisib.

All the secondary endpoints including the safety analysis will be reported using the full population, to analyze data over time all available data will be used (Section 3.6.2). No imputation methods will be performed.

Endpoint #1: Percent change in the sum of target lesion (1 to 3 lesions) volume, as assessed by a central review of imaging scans, as measured by the change between the index date (or up to 24 weeks prior) and key time-points following the index date.

Endpoint #2: Percent change in sum of all measurable lesions (target and non-target) volume, as assessed by a central review of imaging scans, as measured by the change between the index date (or up to 24 weeks prior) and key time-points following the index date.

Endpoint #3: Percent change in the sum of all measurable non-target lesion volume, as assessed by a central review of imaging scans, as measured by the change between the index date (or up to 24 weeks prior) and key time-points following the index date.

In order to comprehensively demonstrate the efficacy of alpelisib treatment on target lesions, the percent change will be evaluated and reported at predefined time points throughout the study period (Section 3.3), under the assumption that a considerable number of patients have been treated for longer than 24 weeks.

Similarly as endpoint #1, the change in all measurable lesions, including the non-target, need to be assessed to confirm the potential benefit of alpelisib.

The percent change in the sum of measurable lesion volume (target and non-target) for each patient from index date to a generic key time point X (with X = 4, 12, 24, 36, 52 etc), will be calculated using the following equation:

$$\frac{\text{Sum}(\text{volume1}_{X\text{weeks}}, \text{volume2}_{X\text{weeks}}, \text{volume3}_{X\text{weeks}}) - \text{Sum}(\text{volume1}_{\text{index}}, \text{volume2}_{\text{index}}, \text{volume3}_{\text{index}})}{\text{Sum}(\text{volume1}_{\text{index}}, \text{volume2}_{\text{index}}, \text{volume3}_{\text{index}})} \times 100\%$$

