The change and percent change in lesion volume will be assessed as a continuous measure over time. A graphical representation, such as box plots at each time-point, will be provided to illustrate changes over time. A by patient graph will also be considered to depict individual trend. Additional information on time windows for each study key-time point following the index date are reported in Section 3.3.

Endpoints related to secondary objective #4: Duration of response (DOR)

Duration of response (DOR) is defined as the time from first documented response, to the date of the first documented disease progression or death due to any cause. This analysis only applies to responders (definition Section 3.5). The start date is the date of first documented

response, and the end date is defined as the date of the first documented disease progression or death due any cause. Patients continuing without event will be censored at the date of their last adequate lesion assessment (i.e. MRI scans performed to assess volumetric measurements).

DOR will be listed and summarized for all patients in the efficacy set with response. The distribution of duration of response will be estimated using the Kaplan-Meier method and the median will be presented along with 95% confidence interval only if a sufficient number of responses is observed.

Endpoints related to secondary objective #5: Description in type of medication and non-drug therapies (e.g., concomitant PROS-related medications, PROS-related surgeries and duration of treatment) over time.

This endpoint will assess the alpelisib exposure pattern in the study population, including any treatment interruption, dose changes and duration of treatment overall during the study period. The number of patients who have at least one dose adjustment, interruption, or discontinuation, and their reasons will be reported where available.

Furthermore, the concomitant utilization of PROS-related medications, such as those prophylactic antibiotics, pain medications and anti-epileptics, as well as PROS-related non-drug treatments, such as ketogenic diets and surgical corsets, will allow to establish an association between the efficacy of alpelisib (as measured by the primary end point) and symptomatic/clinical benefit for the patient.

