3.6.2 Handling of missing data for the secondary endpoints

To report of the secondary endpoint all available data at that specific time point will be used. At each time point the total number of patients with available data will be shown. No imputation methods will be performed. If at the time point a parameter is missing for that patient it will not be reported.

[REDACTED]

4 Appendix

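### Volume change over time (endpoints 1–3) is summarized in a different set of patients in each window, so a trend in the means can appear, in either direction, without any patient changing

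*SAP*

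**What the plan says.** For the secondary endpoints, SAP section 3.6 states that "to analyze data over time all available data will be used". SAP section 3.3 sets the rule for every key time-point: "For each of these time-points or intervals all patients with data available will be used". The denominator follows from it: "The total number of patients in a time interval will be equal to the number of patients with at least one valid assessment" in that window. Section 3.6.2 rules out imputation for the secondary endpoints and adds: "If at the time point a parameter is missing for that patient it will not be reported". A window is displayed once at least 10% of patients have data in it.

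Three features of the study decide who is in a later window.

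- **Discontinuation.** For a patient who stops treatment before the cut-off, "only data reported up to 30 days after the last date of study treatment will be abstracted" (SAP section 1.3; the same rule is in protocol section 6.1).
- **Cut-off.** Patients who started by 23-Sep-2019 "are expected to have 24 weeks of relevant assessments on or before 09-Mar-2020" (SAP section 1.3). Nothing beyond 24 weeks is assured.
- **Imaging practice.** SAP section 3.5.3 attributes variable scan frequency to individual patient need or age, to scans sometimes not being useful for monitoring response, and to institution or insurance policy.

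The summaries for endpoints 1–3 are descriptive statistics and box plots per window. On individual courses the SAP says: "A by patient graph will also be considered to depict individual trend". Protocol section 6.8.2 names a spaghetti plot as an example of the graphics for endpoint 1, and box plots only for endpoints 2 and 3.

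**The concern.** Objectives 1–3 ask for change over time. A row of box plots at Weeks 24, 36, 52 and beyond invites the reader to follow one group of patients through them, but the plan does not follow one group. If patients with little shrinkage stop treatment and leave, the later means look better. If patients doing well are scanned less often, the later means look worse. Neither trend says what happened within patients.

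SAP section 3.6 introduces these summaries with "In order to comprehensively demonstrate the efficacy of alpelisib treatment on target lesions", and protocol section 6.8.1 rests the overall efficacy description on primary and secondary endpoints together. What is at stake is a descriptive trend being read as continuing shrinkage, or as loss of effect, when it may only show who was left. The multiple imputation, the best- and worst-case analyses and the comparison of patients with and without a Week 24 assessment all concern the primary endpoint. None of them helps here.

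**Working it through.** **The plan's own figure.** The documents give no numerical expectation for endpoints 1–3, so there is none to reproduce. The follow-up figure can be checked: 23-Sep-2019 to 09-Mar-2020 is 168 days, and 168 / 7 = 24 weeks. Counting back from the cut-off, a patient must have started by 29-Jul-2019 to reach the opening of the 36-week window (week 32), and by 03-Jun-2019 to reach that of the 52-week window (week 40). With the protocol's planning number of 50 patients, the 10% display rule is met by 5.

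**Composition example (assumed inputs).** Suppose every patient is constant, at −25% (shrunk) or +5% (not shrunk). With *a* shrunk and *b* not shrunk patients scanned, the window mean is (−25*a* + 5*b*) / (*a* + *b*).

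| Scanned (a+b) | Calculation | Window mean | Same patients' Week 24 mean | Paired change |
|---|---|---|---|---|
| Week 24: 20+20 | (−500 + 100) / 40 | −10.0% | – | – |
| Later: 16+16 | (−400 + 80) / 32 | −10.0% | −10.0% | 0 |
| Later: 16+12 | (−400 + 60) / 28 | −12.1% | −12.1% | 0 |
| Later: 16+4 | (−400 + 20) / 20 | −19.0% | −19.0% | 0 |
| Later: 12+16 | (−300 + 80) / 28 | −7.9% | −7.9% | 0 |

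The mean equals 5 − 30*s*, where *s* is the share of shrunk patients among those scanned. Only a change in *s* moves it. Loss that is unrelated to volume change leaves it alone.

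**Range by rate of loss (assumed inputs).** Take 25 patients at −30% and 25 at 0%, with 5% of the shrunk group lost per window over four steps. The mean starts at −15.0%. If the other group loses 5% per window it ends at −15.0%; with 10% it ends at −16.6%, with 20% at −20.0% and with 30% at −23.2%.

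**Simulation (assumed inputs).** 2,000 runs of 50 patients over five windows had no true within-patient change, a mean of −15% and measurement SD 5. Loss was 30% per window after a value above −20% and 5% otherwise. From first to last window the available-case mean moved from −14.9% to −21.8% with between-patient SD 15, from −15.1% to −26.7% with SD 25, and from −14.9% to −31.1% with SD 35. In patients present in all five windows the change from the first window stayed between 0.0 and +0.2 points.

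**The case against.** The plan is more open about attrition than the window means alone suggest. N is shown at each time point (SAP sections 3.3 and 3.6.2), discontinuations and their reasons are presented at key time-points (section 3.4), and all volumetric measurements are listed (section 3.3). An end-of-study window is also reported, and duration of response follows responders individually. The analyses are descriptive, with no hypothesis test, and the primary endpoint is unaffected. The sentence about demonstrating efficacy refers to target lesions and is conditioned on many patients being treated beyond 24 weeks. All of that stands. It makes a change in membership partly visible, but it does not separate it from within-patient change. The end-of-study window, for instance, holds a discontinuer only if a scan falls in its four weeks.

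Four stronger readings are tempting, and the documents do not support them.

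- A reader might infer that the by-patient graph is the only safeguard. The items above show that it is not.
- A reader might infer that the drift must flatter the drug. Need-driven imaging can work the other way, and loss through the cut-off depends on start date, which need not relate to response.
- A reader might take the 9-point drift (−10.0% to −19.0%) as the expected size. It requires losing 16 of 20 non-shrinkers but only 4 of 20 shrinkers. The documents give no discontinuation rate, scan rate or SD.
- A reader might infer that the SAP withdrew a plot the protocol had promised. The protocol offers the spaghetti plot as an example, for endpoint 1 only, and SAP section 2 announces no removal. This is wording to align.

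**Conclusion.** The concern holds in a limited form. Under the written rules the window summaries for endpoints 1–3 can trend up or down through composition alone, and no paired, constant-cohort or longitudinal summary is planned that would show it. In the two-group example the later mean runs from −7.9% to −19.0% around an unchanged −10.0%, and there is no drift when loss is balanced. These figures rest on assumed volume changes and retention. They show that the effect is possible, not how large it will be here. The consequence is for interpretation of objectives 1–3, not for error rates or the primary result. A better summary is available from scans already collected and without a model, so the change is worth making.

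**What to change.** In SAP section 3.6, for each window after Week 24 and for each of endpoints 1–3, keep the available-case summary. Beside it, for patients scanned both in that window and at Week 24, add (a) their Week 24 percent change and (b) the within-patient difference, with n. In the end-of-study window, pair only scans later than the one used for Week 24, because for late starters the two windows overlap.

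In the same section, change the by-patient graph from something to be considered to something that will be provided. This agrees with the spaghetti plot named for endpoint 1 in protocol section 6.8.2.

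The cost is two extra rows per later window in three tables, repeated for the roughly 11-week windows after Week 52, and a smaller paired n. The paired rows remove the composition artefact but not selection: they describe only patients who remain on treatment and are scanned, and the report should say so. Weeks 4 and 12 are not covered by this comparison.

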## **6.9 Handling of missing data**

As this is a retrospective non-interventional study, information may not be systematically collected, resulting in some missing data. Methods of handling missing data for each of the study variables will be detailed in the SAP.

Imaging scans for all measurable lesions may not be available for all patients on the index date. In such cases, the most recent imaging scan conducted during the 12 weeks prior to the index date will be considered as the imaging scan performed on the index date for these patients. This 12 -week window is being utilized based on feasibility assessment of the likelihood of imaging being available at index date and a reasonable time period in which to review imaging data in the pre-index period.

All data available for each patient and each variable will be collected during the pre-index and the study period; appropriate key time-points and associated time windows for the study period (Table 6-1) will be used to analyze the secondary endpoints given there is no common assessment schedule in clinical practice. The number of patients with missing values will be reported.

For the primary analysis, all patients in the efficacy population without missing response will be used (complete case analysis).

Supportive analyses will be performed to investigate the robustness of the primary analysis using the full efficacy population. In particular, a sensitivity analysis will be performed where missing volumetric assessments at Week 24 will be multiply imputed based on a missing at random (MAR) assumption for patients with missing response. The imputation model will include the longitudinal volumetric measurements (i.e. the MRI scans at index date and at Week 48), the measurement at index date, as well as covariates such as age. Additional details will be provided in the SAP.

No imputation will be performed for the non-target lesions, only lesions that have data at index date (or up to 12 weeks prior) and at weeks 24 (+/- 4 weeks) will be used to define progression.

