3.5.2 Handling of missing data for the primary endpoint

As this is a retrospective, non-interventional study, information may not be systematically collected at each time-point of interest, resulting in missing data.

All patients in the efficacy population without a missing response will be used for the primary analysis of the primary endpoint (complete case analysis).

The completeness of the response variable will be enumerated by reporting the following:

- Reasons for missing response at week 24 or 6 months (+/- 4 weeks), including missing imaging scans, as available (e.g., insurance considerations, age considerations, absence of overgrowth, differences in clinical practice) where available will be reported.
- Differences in the patient population with regard to demographic and clinical characteristics (e.g., age, PROS sub-type) will be reported in a table for patients with and without 24 weeks or 6 months (+/- 4 weeks) assessments.

For the primary endpoint, 1 to 3 target lesions identified at index date via central review of imaging scans are considered. If information about volumetric assessment of one or two identified target lesions at index date is missing/non-evaluable at Week 24 time point (24 weeks or 6 months (+/- 4 weeks)), the sum of target lesions volume will be calculated using only the target lesion with paired assessment available.

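### The percent-change equation for secondary endpoints 1 to 3 does not require the same lesions in both sums, and it lists only three volumes for endpoints that cover all measurable lesions

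*SAP*

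**What the plan says.** SAP 3.6 gives a single definition for endpoints 1 to 3: "The percent change in the sum of measurable lesion volume (target and non-target) for each patient" from index to key time point X "will be calculated using the following equation". The equation takes Sum(volume1, volume2, volume3) at week X, subtracts the same three-term sum at index, and divides by the index sum. Endpoint 1 covers 1 to 3 target lesions. Endpoint 2 covers all measurable lesions, and endpoint 3 all measurable non-target lesions; no maximum is stated for either.

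On missing data, SAP 3.6 says that "to analyze data over time all available data will be used". SAP 3.6.2 says "No imputation methods will be performed" and adds: "If at the time point a parameter is missing for that patient it will not be reported".

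The primary endpoint has its own rule. SAP 3.5.2 opens it with "For the primary endpoint, 1 to 3 target lesions identified at index date via central review of imaging scans are considered". If one or two of those lesions cannot be assessed at Week 24, "the sum of target lesions volume will be calculated using only the target lesion with paired assessment available". Protocol 6.9 has a similar rule for non-target lesions: "only lesions that have data at index date (or up to 12 weeks prior) and at weeks 24 (+/- 4 weeks) will be used". That rule serves only to define progression at Week 24.

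**The concern.** The plan foresees that a target lesion may be missing or non-evaluable when others are not, and it handles this for the primary endpoint at Week 24. No such rule is written for endpoint 1 at weeks 4, 12, 36, 52 and later, or for endpoints 2 and 3 at any time point. SAP 3.5.3 expects imaging to be unavailable at some key time points, and scanning followed local practice, so incomplete lesion sets are plausible.

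These endpoints carry weight. SAP 3.6 presents endpoint 1 as showing efficacy on target lesions over the whole study period, and endpoints 2 and 3 as confirming benefit. Protocol 6.8.1 bases the overall efficacy description on primary and secondary evidence together, and Protocol section 9 intends the results for submission to health authorities. There is no control arm in which an artefact of measurement coverage could show itself.

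**Working it through.** The documents give no numerical result on this point, so there is no figure to reproduce. The check evaluates the SAP 3.6 equation when one volume is missing.

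**Inputs.** The equation and the missing-data statements come from SAP 3.6 and 3.6.2, and the paired rule from SAP 3.5.2. Lesion volumes and the rate of incomplete lesion sets are not in the documents. All volumes below are assumptions, shown over a range.

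**Three ways to evaluate the equation when a week-X volume is missing**

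1. *Skip:* the missing term drops out of the week-X sum, but the lesion stays in the index sum.
2. *Strict:* any missing term voids the sum, and the patient has no value at X.
3. *Paired:* both sums use only lesions measured at both times (the SAP 3.5.2 rule).

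**Skip reading, lesion missing at week X.** Let w be the share of index volume that is unscanned and c the true change in the scanned lesions. Then

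apparent change = (1 - w)(1 + c) - 1.

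With c = 0 this is -w.

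| w (assumed) | c = -10% | c = 0 | c = +10% |
|---|---|---|---|
| 5% | -14.5% | -5.0% | +4.5% |
| 10% | -19.0% | -10.0% | -1.0% |
| 20% | -28.0% | -20.0% | -12.0% |
| 1/3 | -40.0% | -33.3% | -26.7% |
| 1/2 | -55.0% | -50.0% | -45.0% |
| 2/3 | -70.0% | -66.7% | -63.3% |

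The paired rule returns the true c in every cell. The strict rule returns no value in any cell.

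With unequal lesions and no true change, index volumes of 200, 60 and 40 give 260/300 - 1 = -13.3% if the smallest is unscanned and 100/300 - 1 = -66.7% if the largest is. Volumes of 100, 100 and 50 give 200/250 - 1 = -20% or 150/250 - 1 = -40%.

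**Skip reading, lesion missing at index.** Take three equal, unchanged lesions of 100, one of them not measured at index: (300 - 200)/200 = +50%. The artefact now points the other way.

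**Which reading does the text support?** The equation always lists three volumes, but a patient may have one or two target lesions. Taken literally, it can be evaluated for such a patient only if empty terms are skipped; a literal strict reading would exclude all of them. Against that, the sentence in SAP 3.6.2 on a missing parameter may mean that the patient's sum goes unreported, because it does not say whether a parameter is one lesion's volume or the sum. The text settles neither.

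**Consistency with the primary analysis.** Suppose one of three target lesions is unscanned at Week 24. The primary endpoint uses the paired sum. For the same patient and visit, endpoint 1 gives a different number under skip and no number under strict.

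**Number of terms.** The equation is introduced for target and non-target lesions together but has three terms. A patient with three target lesions and any measurable non-target lesion already exceeds it for endpoint 2.

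**The case against.** The strongest objection is that the equation is symmetric. The same three terms appear at both times, and nothing says that the week-X sum takes whatever is available while the index sum keeps everything. Counting an unscanned lesion as zero volume would amount to imputing zero, which sits badly with the SAP's statement that nothing is imputed. SAP 3.1 names SAS but no function or missing-value behaviour. Details of the central evaluation are left to the Independent Central Review Charter, which is not among the documents. It would also be odd to form two different target sums at Week 24, and SAP 3.3 lists all volumetric measurements, so gaps could be traced.

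This stands against a stronger reading that a reader might reach: that the formula as written turns unscanned lesions into shrinkage. The SAP permits that calculation but does not prescribe it. A reader might also infer that the error must favour the drug. A lesion missing at week X does push the result towards benefit, but an existing lesion missing only at index pushes it towards growth, and the documents do not say which is more common.

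The objection does not close the gap. No sentence extends pairing to endpoints 1 to 3, and both unpaired readings disagree with the primary analysis at the same visit. The mismatch in the number of volumes does not depend on missing data at all.

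**Conclusion.** The concern holds as an undefined calculation with a specific remedy. For endpoints 1 to 3 the SAP does not say that both sums use the same lesions. Under the skip reading with no true change, the false change for a lesion missing at week X equals minus its share of index volume: -5% to -67% over the assumed range. Under the strict reading nothing is falsified, but patients are lost. The actual size cannot be computed, because the documents give neither lesion volumes nor the frequency of incomplete sets. Separately, the three-volume equation is wrong as written for endpoints 2 and 3.

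Some of these values pass 20%, and a reader might infer that the response rate is inflated. The documents do not support that: the 20% threshold belongs to the primary endpoint, which SAP 3.5.2 protects by pairing. Endpoints 1 to 3 are descriptive and have no threshold or test. The point should be corrected, but it does not put the primary result in doubt.

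**What to change.** Replace the equation in SAP 3.6 and add one sentence. For endpoints 1 to 3 at every key time point X, let P be the set of all lesions in the relevant class (target, all measurable, or non-target; not limited to three) with a volume at both index and week X. Then

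percent change = 100 × [sum over P of volume at X - sum over P of volume at index] / [sum over P of volume at index].

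Set the result to missing if P is empty. Report for each time point the number of patients with at least one unpaired lesion and the number of unpaired lesions.

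The cost is a corrected equation, a sentence and a few counts; no new data are needed. There are two consequences to state. First, the lesions contributing for a patient can differ between time points, which the counts make visible. Second, a lesion that first appears after index has no index volume and stays out of the sum; SAP 3.5.1 already captures new lesions through the response and progression definitions.
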